The initial data from this study (Protocol KD019-101) indicate that subjects with ADPKD receiving tesevatinib have experienced elevations of creatinine without elevations in cystatin C. The median changes from screening values for creatinine and cystatin C from all 9 subjects in the 50-mg dose cohort reveal that creatinine values were increased by 7.5% at Day 3, by 22% at Day 7, and increased by 13% at Day 28. Data after Day 28, including 2 subjects who have received tesevatinib for 16 months, do not indicate any significant ongoing change in creatinine. Cystatin C levels, during the same time periods, did not change (median decreases of 4.5%, 1%, and 4% at Days 3, 7, and 28, respectively). Data from the 8 subjects enrolled into the 100-mg dose cohort, as well as subjects enrolled in subsequent cohorts, exhibited a similar pattern. This increase in

creatinine occurs early and after approximately 7 days, does not continue to increase, similar to the increase in serum creatinine seen with cimetidine. Increases in creatinine were seen in previous clinical studies of tesevatinib. For example, increases in serum creatinine in 10% of subjects were reported in Study XL647-201. However, most of the previous studies were in subjects with malignancies, and in previous studies, cystatin C levels were not evaluated, so increases in serum creatinine that may not represent renal dysfunction were not recognized.

In order to further investigate the effects of tesevatinib on serum creatinine levels, the effects of tesevatinib on a panel of transporter molecules (including OCT2 and MATE) were evaluated in vitro. Preliminary results indicate that tesevatinib potently inhibits MATE1 and MATE2-K transporter proteins. MATE transporter proteins carry creatinine out of kidney proximal tubule cells into the tubule lumen. Inhibition of MATE transporter proteins decreases secretion of creatinine into the proximal tubule lumen and leads to an increase in serum creatinine levels. To demonstrate the reversible nature of the creatinine elevations, subjects on the Phase 1b portion of the study will have study drug held for a one-time drug holiday of at least 14 and up to 28 days with creatinine and cystatin C measurements before and immediately after the drug holiday, as well as a predose PK sample prior to restarting study drug.

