8.2 Inclusion Criteria

A subject must meet the following criteria to be eligible for the study:

- The subject has a confirmed diagnosis of ADPKD based on Ravine's criteria. Subjects
 30 years of age must have at least 2 cysts (unilateral or bilateral) while subjects ≥ 30 years of age must have at least 2 cysts in each kidney (ie, total ≥ 4 cysts).
- 2. Cysts must be at least 1 cm in size to be considered.
- 3. Subject is ≥ 18 but ≤ 62 years of age at time of consent.
- 4. The subject has an eGFR \geq 35 mL/min/1.73 m² and \leq 80 mL/min/1.73 m² using the MDRD-4 variable formula (Appendix A).
- The subject has an htTKV ≥ 1000 mL (htTKV is calculated using total kidney volume obtained from MRI divided by height in meters).
- 6. Subject has the following laboratory values:
 - Platelets >LLN
 - Hemoglobin > 9 g/dL
 - Total bilirubin $\leq 1.5 \text{ mg/dL}$
 - AST (SGOT) $< 2.5 \times$ upper limit of normal (ULN)
 - ALT (SGPT) $< 2.5 \times ULN$
 - $PT/PTT \le 1.5 ULN$
 - Albumin \geq lower limit of normal
 - Amylase within normal limits

- Lipase within normal limits
- 7. The subject has International Normalized Ratio (INR) \leq 1.5, except those subjects taking warfarin who must have INR \leq 3.0.
- 8. The subject has serum potassium levels and serum magnesium levels within the normal range.
- 9. The subject is capable of understanding and complying with the protocol and has signed the informed consent form.
- 10. Female subjects of childbearing potential have a negative pregnancy test at Screening. Females of childbearing potential are defined as sexually mature women without prior hysterectomy or who have had any evidence of menses in the past 12 months. However, women who have been amenorrheic for 12 or more months are still considered to be of childbearing potential if the amenorrhea is possibly due to prior chemotherapy, antiestrogens, or ovarian suppression.
 - Women of childbearing potential (ie, menstruating women) must have a negative urine pregnancy test (positive urine tests are to be confirmed by serum test) documented within the 24-hour period prior to the first dose of study drug.

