14.3.6 Efficacy/Activity

Descriptive statistics, including confidence intervals for GFR, will be presented over time for the Phase 2a cohort. In addition, identical statistics for the change and percent change from baseline GFR over time will be presented with the 6-month change from baseline being of particular interest.

Similar descriptive statistics will be presented for the reciprocal of serum creatinine endpoints.

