Appendix A: Equations to Predict Glomerular Filtration Rate (MDRD-4, CKD-EPI_{2012cys}, and CKD-EPI_{2012Scr-cys})

4-Variable Modification of Diet in Renal Disease (MDRD-4) Equation

High Level Formula for Black or African-American Males:

Estimated GFR =
$$175 \times (Creatinine^{-1.154}) \times (Age^{-0.203}) \times 1.212$$

High Level Formula for Males NOT Black or African-American (any other option):

Estimated GFR =
$$175 \times (Creatinine^{-1.154}) \times (Age^{-0.203})$$

High Level Formula for Black or African-American Females:

Estimated GFR =
$$175 \times (Creatinine^{-1.154}) \times (Age^{-0.203}) \times 1.212 \times 0.742$$

High Level Formula for Females NOT Black or African-American (any other option):

Estimated GFR =
$$175 \times (Creatinine^{-1.154}) \times (Age^{-0.203}) \times 0.742$$

CKD-EPI_{2012cys} Equation to Predict Glomerular Filtration Rate (GFR)

Gender	Scys (mg/L)	Equation
female	≤ 0.8	$133 \times (\text{Scys/0.8})^{-0.499} \times 0.996^{\text{age}} (\times 0.932)$
	> 0.8	$133 \times (\text{Scys/0.8})^{-1.328} \times 0.996^{\text{age}} (\times 0.932)$
male	≤ 0.8	$133 \times (\text{Scys/0.8})^{-0.499} \times 0.996^{\text{age}}$
	> 0.8	$133 \times (\text{Scys/0.8})^{-1.328} \times 0.996^{\text{age}}$

Note: Age is shown as years.

Scr = serum creatinine; Scys = serum cystatin C; CKD-EPI_{2012cys} = cystatin C-based CKD-EPI equation developed in 2012

CKD-EPI _{2012Ser-evs}	Equation	to	Predict	Glomerular	Filtration	Rate	(GFR)
CILD LI IZUIZSCI-CVS	Lquution	·	1 I Cuict	Giomici aiai	I IIII WUIDII	12000	()

Gender	Scr (mg/dL)	Scys (mg/L)	Equation
female	≤ 0.7	≤ 0.8	$130 \times (\text{Scr/0.7})^{-0.248} \times (\text{Scys/0.8})^{-0.375} \times 0.995^{\text{age}} (\times 1.08, \text{ if black})$
		> 0.8	$130 \times (\text{Scr/0.7})^{-0.248} \times (\text{Scys/0.8})^{-0.711} \times 0.995^{\text{age}} (\times 1.08, \text{ if black})$
	> 0.7	≤ 0.8	$130 \times (\text{Scr/0.7})^{-0.601} \times (\text{Scys/0.8})^{-0.375} \times 0.995^{\text{age}} (\times 1.08, \text{ if black})$
		> 0.8	$130 \times (\text{Scr/0.7})^{-0.601} \times (\text{Scys/0.8})^{-0.711} \times 0.995^{\text{age}} (\times 1.08, \text{ if black})$
male	≤ 0.9	≤ 0.8	$135 \times (\text{Scr/0.9})^{-0.207} \times (\text{Scys/0.8})^{-0.375} \times 0.995^{\text{age}} (\times 1.08, \text{ if black})$
		> 0.8	$135 \times (Scr/0.9)^{-0.207} \times (Scys/0.8)^{-0.711} \times 0.995^{age} (\times 1.08, if black)$

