	> 0.9	≤ 0.8	$135 \times (\text{Scr/}0.9)^{-0.601} \times (\text{Scys/}0.8)^{-0.375} \times 0.995^{\text{age}} (\times 1.08, \text{ if black})$
		> 0.8	$135 \times (\text{Scr/}0.9)^{-0.601} \times (\text{Scys/}0.8)^{-0.711} \times 0.995^{\text{age}} (\times 1.08, \text{ if black})$

Note: Age is shown as years.

 $Scr = serum creatinine; Scys = serum cystatin C; CKD-EPI_{2012Scr-cys} = serum creatinine- and cystatin C-based CKD-EPI equation$

CKD-EPI_{2012cys} and CKD-EPI_{2012Scr-cys} Equations abstracted from: Zhu Y, Ye X, Zhu B, Pei X, Wei L, et al. Comparisons between the 2012 New CKD-EPI (Chronic Kidney Disease Epidemiology Collaboration) Equations and Other Four Approved Equations. *PLoS ONE*. 2014. 9(1): e84688. doi:10.1371/journal.pone.0084688

Appendix B: Concomitant Medications Associated With a Risk of QTc(F) Interval Prolongation and/or Torsades de Pointes

Use of these drugs should be avoided in subjects who are receiving KD019. Subjects who require treatment with these drugs should have KD019 held for up to 21 days while receiving the treatment and should be closely monitored for QTc(F) prolongation and potential AEs. This list is not comprehensive and all concomitant medications should be evaluated for potential contribution to QTc(F) prolongation. Refer to the following web site whenever a potential concomitant medication is needed for additional listings and information:

https://crediblemeds.org/index.php?rf=US

Drug Type	Drug Name
Anti-anginal	bepridil
Anti-arrhythmic	amiodarone, disopyramide, dofetilide, ibutilide, procainamide, quinidine, sotalol
Antibiotic	clarithromycin, erythromycin, azithromycin, sparfloxacin, gatifloxacin, moxifloxacin, troleandomycin
Anti-cancer	arsenic trioxide
Anti-infective/pneumocystis pneumonia	pentamidine
Anti-malarial	chloroquine, halofantrine
Anti-nausea	domperidone, droperidol
Anti-psychotic	haloperidol, mesoridazine, thioridazine
Anti-psychotic/anti-emetic	chlorpromazine
Anti-psychotic/Tourette's tics	pimozide
GI stimulant/heartburn	cisapride
Opiate agonist/pain control/narcotic dependence	levomethadyl, methadone

Reference: http://www.arizonacert.org/medical-pros/drug-lists/drug-lists.htm

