3.7 Primary Endpoint Analysis

The primary endpoint for the Phase 1b portion of KD019-101 is safety and tolerability. This will be covered in Section 3.9.

The primary endpoint is annualized change in glomerular filtration rate (GFR) in subjects with ADPKD when treated with tesevatinib. The annualized change in GFR will be calculated as the percent change from baseline divided by total duration in days times 365.25.

This analysis will be done using the mITT population. Descriptive statistics will be provided for each cohort. The annualized GFR will be calculated for the 6, 12, 18 and 24 months timepoints.

GFR will be estimated using three equations; MDRD-4, CKD-EPI_{2012cys}, and CKD-EPI_{2012Scr-cys}.

4-Variable Modification of Diet in Renal Disease (MDRD-4) Equation

High Level Formula for Black or African-American Males:
$\text{Estimated GFR} = 175 \times (\text{Scr}^{-1.154}) \times (\text{Age}^{-0.203}) \times 1.212$
High Level Formula for Males NOT Black or African-American (any other option):
$\text{Estimated GFR} = 175 \times (\text{Scr}^{-1.154}) \times (\text{Age}^{-0.203})$
High Level Formula for Black or African-American Females:

Estimated GFR = $175 \times (\text{Scr}^{-1.154}) \times (\text{Age}^{-0.203}) \times 1.212 \times 0.742$
High Level Formula for Females NOT Black or African-American (any other option):
Estimated GFR = $175 \times (\text{Scr}^{-1.154}) \times (\text{Age}^{-0.203}) \times 0.742$

Note: Age is shown in years. Scr = serum creatinine

CKD-EPI_{2012cys} Equation to Predict Glomerular Filtration Rate (GFR)

Gender	Scys (mg/L)	Equation
Female	≤ 0.8	$133 \times (\text{Scys}/0.8)^{-0.499} \times 0.996^{\text{age}} (\times 0.932)$
	> 0.8	$133 \times (\text{Scys}/0.8)^{-1.328} \times 0.996^{\text{age}} (\times 0.932)$
Male	≤ 0.8	$133 \times (\text{Scys}/0.8)^{-0.499} \times 0.996^{\text{age}}$
	> 0.8	$133 \times (\text{Scys}/0.8)^{-1.328} \times 0.996^{\text{age}}$

Note: Age is shown in years. Scys= serum cystatin

CKD-EPI_{2012Scr-cys} Equation to Predict Glomerular Filtration Rate (GFR)

Gender	Scr (mg/L)	Scys (mg/L)	Equation
Female	≤ 0.7	≤ 0.8	$130 \times (\text{Scr}/0.7)^{-0.248} \times (\text{Scys}/0.8)^{-0.375} \times 0.995^{\text{age}} (\times 1.08, \text{ if black})$
		> 0.8	$130 \times (\text{Scr}/0.7)^{-0.248} \times (\text{Scys}/0.8)^{-0.711} \times 0.995^{\text{age}} (\times 1.08, \text{ if black})$

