	> 0.7	≤ 0.8	$130 \times (\text{Scr}/0.7)^{-0.601} \times (\text{Scys}/0.8)^{-0.375} \times 0.995^{\text{age}} (\times 1.08, \text{ if black})$
		> 0.8	$130 \times (\text{Scr}/0.7)^{-0.601} \times (\text{Scys}/0.8)^{-0.711} \times 0.995^{\text{age}} (\times 1.08, \text{ if black})$
Male	≤ 0.7	≤ 0.8	$130 \times (\text{Scr}/0.9)^{-0.207} \times (\text{Scys}/0.8)^{-0.375} \times 0.995^{\text{age}} (\times 1.08, \text{ if black})$
		> 0.8	$130 \times (\text{Scr}/0.9)^{-0.207} \times (\text{Scys}/0.8)^{-0.711} \times 0.995^{\text{age}} (\times 1.08, \text{ if black})$

	> 0.7	≤ 0.8	$130 \times (\text{Scr}/0.9)^{-0.601} \times (\text{Scys}/0.8)^{-0.375} \times 0.995^{\text{age}} (\times 1.08, \text{ if black})$
		> 0.8	$130 \times (\text{Scr}/0.9)^{-0.601} \times (\text{Scys}/0.8)^{-0.711} \times 0.995^{\text{age}} (\times 1.08, \text{ if black})$

Note: Age is shown in years. Scys= serum cystatin, Scr = serum creatinine

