3.7.2 Post-hoc Endpoint Analysis

3.7.2.1 Slope of the change in eGFR

The slope of the change in the estimated GFR was derived from the individual slopes for each patient using the MDRD-4 equation. Descriptive statistics will be provided for each cohort [REDACTED]. The change from baseline in the estimated GFR will be calculated two ways. The first using the first and last timepoint for each subject and the second using all of the available timepoints.

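### SAP 3.7 prints the male creatinine–cystatin C GFR equation with a constant and cut-point that contradict Protocol Appendix A and, for the cut-point, its own divisor

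*SAP*

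**What the plan says.** SAP 3.7 (Primary Endpoint Analysis) estimates GFR by three equations: MDRD-4, cystatin C alone, and creatinine with cystatin C. It ranks none above the others. In the third table all four male rows carry the constant 130, and the creatinine rows divide at 0.7. The first male row is "130 \times (\text{Scr}/0.9)^{-0.207} \times (\text{Scys}/0.8)^{-0.375".

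Protocol Appendix A gives the same equation with the constant 135 and the creatinine rows divided at 0.9. Its lower male row is "135 \times (\text{Scr/0.9})^{-0.207} \times (\text{Scys/0.8})^{-0.375" and its upper male row is "135 \times (\text{Scr/}0.9)^{-0.601} \times (\text{Scys/}0.8)^{-0.375". The divisors, exponents, age term and race term agree between the documents, and so do all the female rows. The table headers also differ: creatinine is in mg/L in the SAP and mg/dL in Appendix A.

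On the scale of analysis, the SAP states: "The annualized change in GFR will be calculated as the percent change from baseline divided by total duration in days times 365.25". Protocol 14.3.6 calls for GFR over time with confidence intervals, and adds that "identical statistics for the change and percent change from baseline GFR over time will be presented". SAP Listing 16.2.6.1 lists the estimated GFR values.

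**The concern.** The two documents specify different equations for men. The male rows in the SAP appear to have picked up the female constant and cut-point.

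The cut-point error is visible from the SAP table alone. A two-part power curve of this form is continuous only if the cut-point equals the divisor. That holds for female creatinine (0.7 and 0.7) and for cystatin C (0.8 and 0.8). Male creatinine is the exception: it splits at 0.7 but is divided by 0.9. The error in the constant cannot be seen from the SAP alone; it rests on the disagreement with Appendix A.

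A programmer who follows the SAP would produce male GFR values that contradict the protocol in one of the equations named for the Phase 2a primary endpoint. Tesevatinib raises creatinine without a matching rise in cystatin C (Protocol 5.2.2.2.3), so for a man with low creatinine a misplaced cut-point could exaggerate or even reverse the estimated change.

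**Working it through.** The documents state no figure that depends on this equation, so there is nothing to reproduce first. Both male equations were evaluated as printed, reading creatinine in mg/dL. The cystatin C, age and race terms are identical in the two documents and cancel in every comparison between them.

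**1. Level.** With creatinine at or below 0.7, or at or above 0.9, both versions give the same creatinine term, so SAP / Appendix A = 130/135 = 0.963, an error of −3.7%. At GFR 35 this is 35 × 5/135 = 1.3 mL/min/1.73 m²; at GFR 80 it is 80 × 5/135 = 3.0.

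**2. Between 0.7 and 0.9.** The SAP uses exponent −0.601 where Appendix A uses −0.207.
- Jump in the SAP curve at 0.7: (0.7/0.9)^(−0.601 + 0.207) − 1 = +10.4%.
- Level error just above 0.7: (130/135) × 1.104 − 1 = +6.3%. It falls to −3.7% at 0.9.
- The two errors offset at 0.9 × (130/135)^(1/0.394) = 0.818 mg/dL.

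**3. Percent change.** The constant cancels. If both creatinine values lie outside the band, the two versions agree; for example, 0.65 to 0.95 gives −9.5% by both. Over 68,121 pairs of creatinine values from 0.40 to 3.00 mg/dL, none gave a different percent change unless at least one value lay strictly between 0.7 and 0.9.

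To illustrate the possible size, take the Day 28 median creatinine rise in the 50 mg cohort (Protocol 5.2.2.2.3: "creatinine values were increased by 7.5% at Day 3, by 22% at Day 7, and increased by 13% at Day 28") and assume unchanged cystatin C. The baselines are chosen for illustration.

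| Baseline → follow-up (mg/dL) | Appendix A | SAP |
|---|---|---|
| 0.69 → 0.78 (only follow-up in band) | −2.5% | +3.2% |
| 0.80 → 0.904 | −2.7% | −7.1% |
| 0.85 → 0.96 | −5.0% | −7.1% |
| 0.953 or higher, × 1.13 | −7.1% | −7.1% |

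For the second row, Appendix A gives (0.904/0.9)^−0.601 / (0.80/0.9)^−0.207 − 1 = −2.7%, and the SAP gives 1.13^−0.601 − 1 = −7.1%. Annualized from six months (a factor of 2), these become −5.3% and −14.2%.

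**4. Who can fall in the band.** Entry now requires eGFR no higher than 80, "using the MDRD-4 variable formula (Appendix A", and age no higher than 62. Inverting MDRD-4 for a man who is not Black or African-American, the lowest eligible creatinine is (175 × age^−0.203 / 80)^(1/1.154): 0.953 at age 62, 1.030 at 40 and 1.185 at 18. For Black or African-American men these are multiplied by 1.212^(1/1.154) = 1.18. A current entrant's creatinine would therefore have to fall below 0.9, a drop of at least 1 − 0.9/0.953 = 5.6% at age 62 or 1 − 0.9/1.030 = 12.6% at age 40.

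The documents do not give the eGFR limits or creatinine values for men enrolled earlier. Protocol Table 5-1 shows 4 + 4 = 8 men on the two 150 mg schedules and 9 men on 50 mg, the latter not split between Phase 1b and Phase 2a. That leaves 8 to 17 earlier Phase 2a men who might be exposed; how many actually are is unknown.

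**5. Absolute change.** For men staying above 0.9, the planned mean change of −2.5 mL/min becomes −2.5 × 130/135 = −2.41, a difference of 0.09. With 24/61 = 39% men (all earlier cohorts in Table 5-1), a cohort mean shifts by 0.093 × 0.39 = 0.04. The planned 80% half-width is 1.282 × 4.0/√65 = 0.64.

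**The case against.** The discrepancy itself is hard to dispute: 130 stands in all four male rows and 0.7 in both male splits, so a fault in reading the text is unlikely. The objection concerns the consequences.

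The SAP analyses percent change, so the constant drops out. No man can enter under the current criteria with creatinine in the band, and creatinine rises on treatment, away from it. For the SILK cohort, up to 50 of the 65 planned 50 mg subjects, the documents therefore show no evident route to a wrong percent change. The larger discrepancies in the table above use chosen baselines, and no individual creatinine values are reported. The SAP's output list contains no table of GFR levels or absolute changes, so the level error would surface mainly in Listing 16.2.6.1. The effect on a mean absolute change is negligible beside 0.64.

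All of this stands, and it limits the severity. It does not make the SAP equation usable. Protocol 14.3.6 does require GFR levels and absolute changes, although it names no equation. The cut-point is faulty on the SAP's own terms. Earlier Phase 2a men cannot be shown to be outside the band. It is also fair to say that, for the constant, the documents show only that the SAP and the protocol disagree.

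**Conclusion.** The concern holds: the male rows are wrong as written in the SAP and should be corrected before analysis. If they are programmed as printed, male GFR from this equation is 3.7% below Appendix A outside the 0.7 to 0.9 mg/dL band, and between +6.3% and −3.7% off inside it. Percent change can be distorted, and in one illustrated case reversed in sign, but only when a creatinine value falls inside the band. This is not expected for men entering under the current criteria and is of unknown frequency among earlier men.

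The conclusion takes Appendix A as the reference for the constant and mg/dL as the intended unit. The SAP's mg/L is probably a labelling slip, since cut-points of 0.7 and 0.9 fit only mg/dL. Taken literally, it would multiply GFR above the cut-point by about 10^−0.601 = 0.25 in both sexes.

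MDRD-4, the cystatin-only equation and eligibility are not affected. Nor is the post-hoc slope in SAP 3.7.2.1, which is "derived from the individual slopes for each patient using the MDRD-4 equation".

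**What to change.** In SAP 3.7, replace the four male rows of the creatinine–cystatin C table with those of Protocol Appendix A (constant 135, creatinine split at 0.9) and change the creatinine header to mg/dL. Then check the analysis program against the corrected table, with at least one male test value in each creatinine range, including one between 0.7 and 0.9. The cost is one table correction and one check of a derivation; no new data are needed.

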3.7.1 Secondary Endpoint Analyses

3.7.1.1 Total Kidney Volume

The annualized percent change from height adjusted baseline in total kidney volume (hTKV) will be summarized by cohort and study using the mITT population. hTKV will be determined by MRI at screening (baseline measurement), at the 6-month visit, and every 6 months thereafter. Descriptive statistics will be provided for each timepoint and cohort [REDACTED]. The annualized percent change from baseline will be calculated as the percent change from baseline divided by total duration in days times 365.25.

3.7.1.2 Serum Creatinine

The annualized percent change from baseline in the reciprocal of serum creatinine will be summarized by cohort using the mITT population. Descriptive statistics will be provided for each cohort [REDACTED]. The change from baseline in the reciprocal of serum creatinine will be calculated using the first and last timepoint for each subject. The annualized percent change from baseline will be calculated as the percent change from baseline divided by total duration in days times 365.25.

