	Screening		Early	Treatment 1	Period ^b		Drug Holiday Period	Month 2	Monthly Follow-Up Treatment Period ^c	End of Study ^d
Assessments	(-28 Days)	Day 1	Day 7 (±1 day)	Day 14 (±1 day)	Day 21 (±1 day)	Day 28 (±1 day)	4 Weekly Visits Beginning at Day 28 Visit (± 1 day)	4 Weekly Visits Beginning at Month 2 Visit (± 1 day)	Every 28 Days Beginning at Month 3 (± 3 days)	(30 Days from Last Dose) (± 3 days)
Informed consent	X							, ,		
Medical and PKD history (including genotype, if available)	X									
Physical examination (including weight) ^e	X	X	X	X	X	X		X°	X	X
Vital signs ^t	X	X	X	X	X	X		X°	X	X
Supine 12-Lead ECG ^g	X	X	X	X	X	X		X°	X	X
Clinical laboratory tests ^h	X	X	X	X	X	X	X	X°	X	X
Ocular evaluation	X								X	
Echocardiogram ^J	X					X			X	X
Pregnancy test ^k	X	X				X				X
MRI	X									X
Study drug administration		X X	X	X	X	X			X	
Concomitant medications ^p	X	X	X	X	X	X	X	X	X	X

Table 4-1: Schedule of Events for Subjects Enrolled in the Safety in Larger Kidneys (SILK) 50 mg Daily Portion of the Study

	Screening		Early	Treatm	ent Pe	eriod ^b		Drug Holiday Period	Month 2	Monthly Follow-Up Treatment Period ^c	End of Study ^d
Assessments	(-28 Days)	Day 1	Day 7 (±1 day)	Day (±1 da		Day 21 (±1 day)	Day 28 (±1 day)	4 Weekly Visits Beginning at Day 28 Visit (± 1 day)	4 Weekly Visits Beginning at Month 2 Visit (± 1 day)	Every 28 Days Beginning at Month 3 (± 3 days)	(30 Days from Last Dose) (± 3 days)
Adverse events ^p		To b	e collected j	from the	time i	nformed co	nsent signed	l until 30 days aft	ter last dose of s	tudy drug.	
PK sampling ^m		X	X	 	X	X	X		X°		
Plasma concentration								X	X		
Dispense/Collect study drug		X	X	X	X	X	X			X°	X

- a. Screening evaluations may be combined with Day 1 pre-treatment laboratory evaluations if both are done within 4 days before first dose of study drug.
- b. All protocol-specified clinic visits during the Treatment Period should occur within ± 1 day of the nominal visit day unless otherwise specified.
- c. Follow-up Treatment Period visits to be performed monthly (every 28 ± 1 day). For those subjects continuing on study beyond 12 months, visits will occur every 2 months \pm 3 days.
- d. End-of-Study visit is to be performed 30 days (± 3 days) after last dose of study drug.

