3.2 Analysis Populations

The following populations will be analyzed:

Modified Intent-to-treat (mITT) Population: The primary population for efficacy analyses will be a Modified Intent-to-treat (mITT) Population. For KD019-101 it is defined as all subjects who completed 28 days (for subjects in the Phase 2a portion of the study this will be 25 or 26 days in the Monday/Thursday and Monday/Wednesday/Friday cohorts, and 28 days in the 50 mg daily dosing cohort).

[REDACTED]

The mITT Population will be used for tables of demography, baseline characteristics, and efficacy.

Safety Population: The Safety Population is defined as all subjects who receive at least 1 dose of tesevatinib.

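### The first-to-last annualization of reciprocal creatinine (and of the first eGFR slope) does not yield a yearly rate: the result depends on when follow-up ended and whether the last sample was on drug

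*SAP*

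**What the plan says.** For the secondary endpoint, SAP 3.7.1.2 says: "The change from baseline in the reciprocal of serum creatinine will be calculated using the first and last timepoint for each subject". It continues: "The annualized percent change from baseline will be calculated as the percent change from baseline divided by total duration in days times 365.25". Results are summarized by cohort in the mITT population. The section sets no minimum interval, visit window or weighting, and no rule on whether the last value must be on drug.

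SAP 3.7.2.1 describes two ways of computing the post-hoc MDRD-4 change: "The first using the first and last timepoint for each subject and the second using all of the available timepoints". The first shares the design of 3.7.1.2.

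On mITT entry, SAP 3.2 says "it is defined as all subjects who completed 28 days", with 25 or 26 days in the intermittent cohorts. By contrast, SAP 3.7 evaluates the primary GFR endpoint at 6, 12, 18 and 24 months.

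Protocol 5.2.2.2.3 gives medians for the nine subjects in the 50 mg cohort: "creatinine values were increased by 7.5% at Day 3, by 22% at Day 7, and increased by 13% at Day 28". Later data "do not indicate any significant ongoing change in creatinine", and cystatin C did not rise. The synopsis attributes the rise to MATE transporter inhibition and expects it to reverse.

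Table 4-1, footnote d, says the "End-of-Study visit is to be performed 30 days" after the last dose. Protocol 9.7 includes serum chemistry at that visit, and Protocol 10.1 seeks those data from everyone who discontinues. SILK subjects also stop drug for 28 days after their first 28 days of treatment, then restart at Month 2 (Protocol 9.2.3 and 9.2.4).

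**The concern.** Dividing a change by elapsed time gives a rate only if the change builds up over time. The protocol describes a step that is complete within weeks and then flat. Divided by elapsed time, such a step measures how long the subject was followed rather than how fast the disease progressed.

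The undefined last value adds a second problem. One subject's last sample may be on drug and carry the whole step. Another's may be the End-of-Study sample, with the step largely gone. The cohort summary would mix the two without distinguishing them.

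At stake is whether the mean in Table 14.3.3, and the first version of the eGFR slope, can be read as yearly progression.

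**Working it through.** **The plan's own figure.** The SAP gives no precision figure for reciprocal creatinine. Its only one is for 6-month GFR change (SAP 3.1.2): an 80% interval of ±0.64 mL/min with n = 65 and SD 4.0. This reproduces: 1.2816 × 4.0/√65 = 0.636, or 0.642 with t on 64 df.

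**Inputs.** Creatinine rise of 13% at Day 28 (Protocol 5.2.2.2.3); half-life of about 70 hours (Protocol 5.4.2); End-of-Study visit 30 days after the last dose; treatment up to 24 months. Duration is counted from the first dose, because the SAP does not state the origin.

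**Step alone, last value on drug, no progression.** The change in 1/creatinine is 1/1.13 − 1 = −11.5%. Annualized, it is −11.5% × 365.25/T:

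| Last on-drug value | Multiplier | Annualized |
|---|---|---|
| Day 25 | 14.6 | −168%/yr |
| Day 28 | 13.04 | −150%/yr |
| Day 56 | 6.52 | −75%/yr |
| 6 months | 2.0 | −23%/yr |
| 12 months | 1.0 | −11.5%/yr |
| 24 months | 0.5 | −5.8%/yr |

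From Day 28 to 24 months the same step differs 26-fold through duration alone.

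**Last value at End-of-Study.** 30 × 24/70 = 10.3 half-lives, which leaves about 0.1% of the drug. If the rise reverses as the protocol expects, the step contribution is roughly zero.

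**Effect on the mean.** The documents give no dropout rate, so the following is an assumption: 5 of 65 leave at Day 28 and 60 reach 24 months.
- With no End-of-Study samples, the step-only mean is (5 × −150.1 + 60 × −5.75)/65 = −16.9%/yr, against −5.8%/yr with no leavers.
- In a cohort of 10 (the size of the Monday/Thursday cohort), one such leaver gives (−150.1 + 9 × −5.75)/10 = −20.2%/yr.
- If all 65 attend End-of-Study, the step largely goes but the noise does not. Last values fall at Day 58 (28 + 30) for leavers and Day 760 (730 + 30) for completers. With equal measurement error per subject, each annualized value has variance proportional to 1/T². Leavers contribute 5/58² = 0.001486 and completers 60/760² = 0.000104, so the 5 leavers carry about 93%. Against 65/760² = 0.0001125 with no leavers, the SE ratio is √(0.001590/0.0001125) ≈ 3.8.

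**Step against an underlying decline.** Assume the SAP's −2.5 mL/min per 6 months at a mid-range eGFR of 57.5. That is −8.7%/yr in eGFR and, through the MDRD-4 exponent, −7.6%/yr in 1/creatinine. At 24 months on drug with no leavers, the step is 5.75/(5.75 + 7.58) = 43% of the result. For baseline eGFR of 80 down to 35 the underlying figure is −5.4 to −12.5%/yr, and the share runs from 51% down to 32%.

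**The case against.** Four points have force.

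- **Early leavers are asked for an off-drug sample.** Protocol 10.1 and 9.7 seek End-of-Study laboratory data from everyone who discontinues. Read literally, a Day 28 leaver's last value falls near Day 58, off drug, with little step left. This stands against using −150%/yr or −16.9%/yr as expected results. It does not rescue the rule: the SAP never says which sample counts, and the noise from short intervals remains.
- **The median is reported** (SAP 3.1.3.1). It resists a few leavers: with the assumed underlying decline it stays at −13.3%/yr with none or three leaving at Day 28. But that figure still contains the step.
- **Other analyses help.** The primary endpoint uses fixed times and includes a cystatin C-only equation, SAP 3.8.2 summarizes laboratory changes by visit, and the drug holidays examine reversibility. SAP 3.7.2.1 adds an all-timepoints calculation, but only for eGFR and also without an on-drug rule.
- **The endpoint is secondary and descriptive**, in an open-label, nonrandomized study with no test attached to it. This limits the severity.

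A reader might infer that a handful of early leavers will supply nearly all of the mean. The documents do not support that. In the five-leaver scenario without End-of-Study samples, they supply 750/1,095 = 68% of the step-only mean, and that needs all five to miss the visit. The matching figures of 98% of the variance and a sevenfold SE count equal measurement error only and ignore true differences in slope between subjects. The same limit applies to the 93% and 3.8-fold figures above.

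**Conclusion.** The concern holds for SAP 3.7.1.2 and for the first calculation in SAP 3.7.2.1. As written, the rule does not produce a yearly rate. With no progression, a 13% rise gives −150%/yr at Day 28, about −23%/yr at 6 months and −5.8%/yr at 24 months on drug, and roughly nothing at End-of-Study.

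This rests on a 13% median from nine subjects, on the reported plateau, and on reversibility that the protocol expects but had yet to demonstrate. The effect on the mean depends on an assumed number and timing of leavers and on their attendance at End-of-Study.

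It would go too far to say that there is no follow-up floor, since mITT entry sets one at 25 to 28 days, or that the primary result fails for this reason. The primary endpoint's fixed times avoid the early-leaver problem, although its MDRD-4 version still contains the step. This is a should-fix.

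**What to change.** In SAP 3.7.1.2, and for the first calculation in 3.7.2.1, replace the two-point annualization with a slope from a linear mixed model (random intercept and slope) fitted to on-drug, steady-state values only.

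- Start at Day 28 or later. After any drug holiday or dose change, use values only once at least 28 days have passed since the restart or change. For SILK this means from Month 3.
- Exclude from the slope the holiday values, the Month 2 pre-dose value, the weekly values after the Month 2 restart, and End-of-Study values. Without this, the renewed rise in SILK (up to 50 of the 65 subjects at 50 mg daily) would put the step back into the slope.
- Report the baseline-to-Day 28 step separately.
- Report the change from off-drug baseline to off-drug End-of-Study as a supportive like-for-like comparison.

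Do not rely on a 6-month minimum with the last on-drug value. It removes the early leavers but keeps the step, about −23%/yr at 6 months.

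The cost is SAP wording and one extra model on data already collected. The downside is that subjects who leave early contribute little or nothing to the slope.
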